7.9.2. Archive Sample

An archive serum sample will be collected pre-dose on Day 0 and at the End-of-Study Assessment. Archive serum samples will be sent to the central laboratory for storage at -70°C and later by batch shipment to a central laboratory archive for storage at -70°C or lower for 15 years. The archive sample serves as a safety measure for subjects receiving human plasma-derived product, for investigation of risk factors which may potentially be identified in the future.

7.10. Recording Laboratory Results

All laboratory tests, except for the urine dipstick pregnancy test on Day 0, will be performed at a central laboratory. Test results will be emailed to the investigator. All reports must be reviewed by the investigator as soon as possible after receipt, and printed, signed and dated by the investigator.

Abnormal laboratory values considered to be clinically significant by the Investigator must be repeated as soon as possible after receiving the laboratory report to rule out laboratory error. Any values outside the normal range should be assessed for clinical significance, and any clinically significant results must be commented upon by the investigator.

7.11. Restrictions

There are no restrictions on study subjects, except for certain concurrent medications ([Section 6.4](#)).

8. OUTCOME MEASURES

8.1. Efficacy Measures

8.1.1. Primary efficacy endpoint

The primary efficacy endpoint is to demonstrate non-inferiority of BPL HRIG compared to an FDA-licensed HRIG product, in terms of:

- the proportion of subjects with anti-rabies antibody titer of ≥ 0.5 IU/mL on day 14 after administration of BPL HRIG and vaccine / active comparator and vaccine using a non-inferiority margin 10%.

8.1.2. Secondary efficacy endpoints

The following secondary efficacy endpoints will be assessed:

- 1) Assessment of AUC_{0-7d} for BPL HRIG and vaccine versus comparator HRIG and vaccine using a non-inferiority margin of 20%.
- 2) Comparison of the geometric mean titers (GMTs) for anti-rabies antibody titer at Days 3, 5, 7, 14, and 28 after administration of BPL HRIG and vaccine versus comparator HRIG and vaccine.
- 3) The proportion of subjects reaching anti-rabies antibody titer of ≥ 0.5 IU/mL at Days 3, 5, 7, 14, 28, 49, and 140 after administration of BPL HRIG and vaccine versus comparator HRIG and vaccine.
- 4) The proportion of subjects reaching anti-rabies antibody titer of \geq the lower limit of quantification (LLOQ) of the assay at Days 3, 5, 7, 14, 28, 49 and 140 after administration of BPL HRIG and vaccine versus comparator HRIG and vaccine.
- 5) Comparison of the geometric mean titers (GMTs) for anti-rabies antibody titer at Days 14, 28, 49, and 140 after administration of BPL HRIG and vaccine versus comparator HRIG and vaccine to assess the inhibitory effects of BPL HRIG on active immunization relative to that of the comparator HRIG.

8.1.3. Exploratory efficacy endpoints

The following PK parameters for anti-rabies antibody concentrations for both treatment groups will be assess as an exploratory endpoint:

- C_{max} [IU/mL]
- T_{max} [day]

- area under the concentration vs time curve to the last measurable concentration (AUC_{0-t}) [$\text{day} \cdot \text{IU}/\text{mL}$]
- apparent terminal rate constant (λ_z) [day^{-1}]
- $AUC_{0-7 \text{ days}}$ [$\text{day} \cdot \text{IU}/\text{mL}$]
- area under the concentration vs time curve to infinity ($AUC_{0-\infty}$), if appropriate
- $C_{\text{max}}/AUC_{0-\infty}$ [or C_{max}/AUC_{0-t} if $AUC_{0-\infty}$ cannot be estimated]
- half-life ($t_{1/2}$), if appropriate

8.1.4. Rabies virus neutralizing antibody

Rabies virus neutralizing antibody (RVNA) levels will be measured at [REDACTED] by the rapid fluorescent focus inhibition test (RFFIT). This serum neutralization test measures the ability of rabies specific antibodies to neutralize rabies virus and prevent the virus from infecting cells, and is the current gold standard serological assay^{3,8}. The WHO 2nd international reference serum for rabies immunoglobulin will be used to titrate as a standard reference each time serum samples are tested. This reference serum can vary in titer level for each batch of testing. Therefore serum samples at each PK timepoint (pre-dose on Days 0, 3, 5, 7, 14, 28, 49 and 140) will be batched by subject, tested for rabies RVNA titer after the subject's study completion, and reported in IU/ml.

The lowest RVNA level that can be accurately and precisely (the lower limit of quantification) measured at [REDACTED] is approximately 0.1 IU/mL. A RVNA level of equal to or above 0.5 IU/mL is globally recognized as indicating adequate vaccine response^{4,9}.

The laboratory staff will be blinded to study treatment. Details for collection and processing of each blood sample will be documented separately in the Laboratory Manual.

8.2. Safety Assessments

The following will be used to assess the safety of BPL HRIG and vaccine, versus comparator HRIG and vaccine:

- Adverse events
- Injection site observations
- Viral serology
- Serum biochemistry, hematology and urinalysis
- Markers of hemolysis
- Physical examination

- Vital signs

The following additional tests will additionally be performed:

- pregnancy tests (for females of childbearing potential).

8.2.1. Adverse Events

All adverse events that appear or worsen during the study, from the time of signing informed consent, will be recorded in the CRF. If a subject has a recurring condition, then this should be recorded at the Screening Visit in the Medical History pages of the CRF. Fluctuations or re-occurrences of the condition, that are considered normal for that subject and are recorded in the medical history, and need not be reported as an adverse event. However, if the condition were to deteriorate during the study this would then be recorded as an adverse event.

Adverse events will be reported in terms of their type, duration, treatment and/or severity.

For further information on the definition and reporting of adverse events, see [Appendix A](#).

8.2.2. Injection Site Observations

Each HRIG and vaccine injection site will be examined, and injection site observations will be assessed, pre-dose and 30 min [\pm 5 min] post-dose on Day 0 and at each subsequent clinic visit unless no symptoms are observed.

For injection site reaction (ISR) assessment criteria, refer to the table below:

Local Reaction to Injectable Product	Mild (Grade 1)	Moderate (Grade 2)	Severe (Grade 3)	Potentially Life Threatening (Grade 4)
Pain	Does not interfere with activity	Repeated use of non- narcotic pain reliever > 24 hours or interferes with activity	Any use of narcotic pain reliever or prevents daily activity	Emergency room (ER) visit or hospitalization
Tenderness	Mild discomfort to touch	Discomfort with movement	Significant discomfort at rest	ER visit or hospitalization
Erythema/Redness *	2.5 – 5 cm	5.1 – 10 cm	> 10 cm	Necrosis or exfoliative dermatitis
Induration/Swelling **	2.5 – 5 cm and does not interfere with activity	5.1 – 10 cm or interferes with activity	> 10 cm or prevents daily activity	Necrosis

* In addition to grading the measured local reaction at the greatest single diameter, the measurement should be recorded as a continuous variable.

** Induration/Swelling should be evaluated and graded using the functional scale as well as the actual measurement.

For the complete guidance (see Appendix A, Section 7): Toxicity Grading Scale for Healthy Adult and Adolescent Volunteers Enrolled in Preventive Vaccine Clinical Trials²⁵ :

All injection site reactions (ISR) will be recorded and graded on the ISR eCRF page. However, the investigator will determine if these are AEs. Injection site reactions will be recorded as AEs when the sign/symptoms require concomitant medications, or have an impact on the general condition of the subject as judged by the Investigator. The investigator will use their judgement to record the severity of the AE, using the appended toxicity scale to guide their assessment.

8.2.3. Viral Serology

Serum samples for viral serology testing will be collected at the Screening Visit and at the End-of-Study Assessment. Subjects with a positive serological test for HIV 1&2, HCV or HBsAg at the Screening Visit will be excluded from the study.

Samples will be tested for the following panel of serological markers:

- Anti-HIV1
- Anti-HIV2
- HBsAg
- Anti-HCV

In addition, a reserve sample will be taken pre-dose at the Baseline Visit and at the End-of-Study Assessment specifically for nucleic acid testing (NAT) if required (see below).

If any of the above serological tests are positive at the End-of-Study Assessment, suggesting a change in viral status of the subject, the sample will be tested by NAT (reflex testing). If a change in viral status is confirmed by NAT, the central laboratory will inform the investigator, Sponsor and the designated CRO within one business day. The reserve samples taken pre-dose at the Baseline Visit and at the End-of-Study Assessment will then be tested in the same laboratory in the same batch.

8.2.4. Serum Biochemistry

Blood samples for serum biochemistry assessments will be collected at the Screening Visit and at the End-of-Study Assessment. Results at the Screening Visit will be used to determine eligibility for the study. The following variables will be assessed for each biochemistry sample collected:

- Albumin

- Alkaline phosphatase (ALP)
- Alanine transferase (ALT)
- Aspartate aminotransferase (AST)
- Blood Urea Nitrogen (BUN)
- bicarbonate
- Bilirubin (direct and total)
- Calcium
- Chloride
- Creatinine
- Creatinine Phosphokinase (CPK)
- Gamma-glutamyl-transferase (GGT)
- Glucose
- Lactate dehydrogenase (LDH)
- Potassium
- Sodium
- Total protein

8.2.5. Hematology

Blood samples for hematology assessments will be collected at the Screening Visit and at the End-of-Study Assessment. Results at the Screening Visit will be used to determine eligibility for the study. The following variables will be assessed for each hematology sample collected:

- Hemoglobin
- Hematocrit
- Red blood cell count
- White blood cell count (total and differential)
- Mean cell volume
- Mean corpuscular hemoglobin concentration
- Platelet count

8.2.6. Urinalysis

Urine samples will be collected for urinalysis, including microscopic examination, at the Screening Visit and at the End-of-Study Assessment. Microscopic examination will be

performed in case of positive dipstick results or abnormal findings. Significant abnormalities at the Screening Visit will exclude the subject from the study.

8.2.7. Markers of Hemolysis

Blood samples for the following markers of hemolysis will be collected pre-dose on Days 0 and 3:

- direct Coomb's test (DCT)
- serum lactate dehydrogenase (LDH)
- plasma free hemoglobin
- serum haptoglobin
- serum bilirubin

A urine sample for urine hemosiderin will be collected at the same timepoints.

If the DCT result at Day 3 is positive or not available by Day 5, blood and urine samples will be collected pre-dose on Day 5 for testing of all the above markers, as well as an unscheduled CBC. If any result at Day 5 is suggestive of hemolysis (*i.e.*, positive DCT; plasma free hemoglobin, LDH, serum bilirubin, or urine hemosiderin above the normal reference range; haptoglobin below the normal reference range) all markers including CBC will be tested pre-dose at Day 7. Similarly, if any result at Day 7 is suggestive of hemolysis; all markers including CBC will be tested pre-dose at Day 14.

Markers of hemolysis will be reviewed regularly by the medical monitor, and any potential signs of hemolysis will be reported to the investigator, sponsor and dedicated CRO by the central laboratory within one business day.

8.2.8. Vital Signs and Body Temperature

Vital signs will be assessed at Screening, Day 0, Day 28, and Day 49 and at the End-of-Study Assessment. Vital signs will include the following assessments:

- Sitting blood pressure (mmHg) after a 5-min rest.
- Pulse rate (bpm).
- Respiration rate (breaths/respirations per minute).

Results at the Screening Visit will be used to determine eligibility for the study. Evidence of uncontrolled hypertension (systolic blood pressure of >150 mmHg, and/or diastolic blood pressure of >100 mmHg), or heart rate >120 beats/min will exclude the subject from the study.

Oral body temperature will be assessed pre-dose on Days 0, 3, 7, 14 and 28. If the subject is febrile (oral temperature $>38.0^{\circ}\text{C}$ [100.4°F]) or has an acute illness at Day 0, their enrollment must be re-scheduled (see [Section 7.3.1](#)). If re-scheduled, Day 0 must be within 28 days of all screening procedures; if outside of this window the subject must undergo a repeat screening visit. A new subject number will be assigned. (See SRM for instructions on repeat screening).

If the subject is febrile at any subsequent visit, active rabies vaccine must not be given. The subject may continue in the study but should receive no further doses of active rabies vaccine and will not be eligible for the per protocol population.

8.2.9. Physical Examination

A physical examination will be performed at the Screening Visit, on Day 49, and at the End-of-Study Assessment. The following body systems will be examined: Head, ears, eyes, nose, throat, chest, cardiovascular, respiratory, abdomen, musculoskeletal, skin and general appearance.

In addition, a 12-lead ECG in a semi-recumbent position following at least 5 minutes of rest will be performed at Screening and the End-of-Study Assessment. Results at the Screening Visit will be used to determine eligibility for the study. Based upon the investigator's judgement, significant abnormalities will exclude the subject from the study.

Any changes in physical examination or ECG from the Screening assessment will be recorded, and any adverse changes will be reported as adverse events.

Body weight and height will be measured at Screening, and body weight only will be repeated pre-dose on Day 0 and at the End-of-Study Assessment. Body weight at Screening or Day 0 which exceeds 95.5 kg will exclude the subject from the study.

8.2.10. Pregnancy Test

A pregnancy test will be performed on all females of child-bearing potential (*i.e.* all those who are not more than 1 year post-menopausal or surgically sterilized). Pregnancy testing will be performed on a serum sample at the Screening Visit, by the central laboratory. Pregnancy testing will be repeated on a urine sample pre-dose at the Baseline visit (Day 0) and serum sample at End-of-Study Assessment by the central laboratory. A negative result at screening and Day 0 must be obtained to confirm the subject is eligible for the study.

9. WITHDRAWAL OF SUBJECTS

Subjects may stop study treatment for any of the following reasons:

- Withdrawal of consent.
- Significant protocol deviation.
- Occurrence of an adverse event which interferes with the subject's ability to continue in the trial.
- Occurrence of adverse events (AEs) not compatible with the continuation of subject participation in the study, in the investigator's opinion (e.g. anaphylactic or other severe/serious reaction to injection).
- Investigator's request.
- Pregnancy. If pregnancy occurs, the subject should be monitored and the outcome of delivery reported.
- Requirement for therapeutic intervention prohibited by the protocol, for example, immunosuppressive agents.
- Potential exposure to the rabies virus during the study, which would necessitate treatment with licensed HRIG.
- Presenting with fever (oral temperature $>38.0^{\circ}\text{C}$ [100.4°F]) on Day 3, 7, 14 or 28.
- Premature termination of the trial by BPL (e.g. if special circumstances concerning the IMP or BPL occur, making further treatment of subjects impossible, or if serious adverse events occur that are considered to make further treatment of subjects impossible). If this occurs, BPL or BPL's representatives will notify the regulatory authorities, ethics committees and investigators of the reason for premature study termination, within 15 days from the study being halted.
- Reason not provided (subject lost to follow-up)

The clinical investigator may also remove a subject if, in his/her opinion, it is in the best interests of the subject. In exceptional circumstances relating to safety, the sponsor may withdraw subjects at any time.

Subjects are free to withdraw from the study at any time without providing reason(s) for withdrawal and without prejudice to further treatment. The reason(s) for withdrawal will be documented where possible, particularly where withdrawal is a consequence of an adverse event (see [Appendix A](#)). The subject's primary care physician will be informed of the reason for withdrawal if follow-up care is needed for safety. The subject will be informed if this is required.

Data collected up until a subject's withdrawal from the study will be used in the analysis. Data on screen failures will be collected.

Subjects withdrawing from the study will be requested to complete the same End-of-Study assessments as subjects completing the study according to the protocol, particularly safety assessments. If there is a medical reason for withdrawal, the subject will remain under the supervision of the investigator until in satisfactory health or the subject's condition has stabilized.

Reasonable efforts will be made to contact subjects who are lost to follow-up. These efforts must be documented in the subject's medical records.

10. DATA ANALYSIS**10.1. Source Data**

The collection and analysis of high quality data is dependent on accurate documentation in the study subjects' hospital notes, to allow accurate verification of CRF data. See [Appendix B](#) (Administrative Requirements) for more detail on the recording of data in subject notes and maintenance of other study documents.

10.2. Data Recording

All data from the study will be entered into a eCRF at the study site. All key data must be entered into the subjects' medical records before they are entered in eCRF (see [Appendix B](#), Section 11.4).

10.3. Statistical and Analytical Plans

All tables, figures and listings will be produced using SAS (v9.4 or a more recent version).

Unless otherwise stated, categorical data will be presented using counts and percentages, whilst continuous variables will be presented using the mean, 95% confidence interval for the mean, standard deviation (SD), median, minimum, maximum, number of subjects (n) and number of missing subjects or data points. Minima and maxima will be quoted to the number of decimal places as recorded in the CRF; means, SDs and medians will be quoted to one further decimal place. Percentages will be rounded to one decimal place.

Subjects who withdraw from the analysis will have their data analyzed to the point of withdrawal.

All data will be listed. More information is in the statistical analysis plan for the study.

10.4. Analysis Populations

The following analysis populations will be defined for this study.

Intent-to-Treat (ITT) Population

The intent-to-treat (ITT) population will include all randomized subjects. All analyses will be performed using the ITT population.

Safety Population

The safety population will be defined as all subjects who receive at least one dose of BPL HRIG / comparator HRIG. Safety data will be analyzed up to the point of withdrawal for applicable subjects. The safety population will be used for all safety analyses.

Per Protocol Population

The per protocol population will be split into the primary and secondary PK populations.

The **primary PK population** will be defined as all subjects who receive the full dose of BPL HRIG / comparator HRIG and the first 3 doses of active rabies vaccine on Visits 2, 3, and 5, and for whom the PK sample at Visit 6 is taken. This population will be used for the primary PK analysis and selected secondary analyses.

The **secondary PK population** will be defined as all subjects who receive the full dose of BPL HRIG / comparator HRIG and all 5 doses of active rabies vaccine and for whom all required PK samples are taken. This population will be used for selected secondary PK analyses and the exploratory PK analysis.

Subjects with a pre-dose RVNA of \geq the LLOQ will be excluded from all analyses.

Subjects not meeting eligibility criteria or for whom major protocol deviations are reported may be excluded from the per protocol population if considered to potentially impact on the PK analysis. Any such cases will be fully justified in the clinical study report.

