10.6. Safety Analysis

The safety analysis will be based on the safety population. The general strategy of the safety evaluation will be to examine the summaries for any clinically relevant imbalance of safety events between the treatment groups. Safety parameters for the two treatment groups will be compared descriptively. Summary data will be presented by Treatment Group. No formal hypothesis testing will be carried out.

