10.6.1. Adverse Events

Adverse events (AEs) will be reported by the MedDRA system organ class and preferred term. Only treatment-emergent AEs, defined as those events with onset date from dosing with BPL HRIG / vaccine or comparator HRIG / vaccine will be included in the summary tables. All AEs will be included in the data listings.

Treatment-related AEs will be defined as events recorded as having a possible, probable or very likely/certain causality to treatment. AEs leading to withdrawal will be defined as events where the subject's participation in the study was discontinued as a result of the AE.

AEs will be summarized descriptively for all subjects and by treatment group. The denominator used for the calculation of percentages will be the number of subjects in the safety population per treatment group. For all AE summaries described below, counting will be performed by subject and event. For counts by subject, subjects experiencing the same event more than once

will have that event counted only once within each system organ class and once within each preferred term.

The following summaries of treatment-emergent AEs will be provided:

Summary of AEs

- 1) The number and percentage of subjects reporting AEs, serious AEs, study medication related AEs, AEs leading to withdrawal and AEs leading to death.
- 2) The number of AEs, serious AEs, study medication-related AEs, AEs leading to withdrawal and AEs leading to death.

Summary of AEs by Severity of Event

The number and percentage of subjects reporting AEs, and study medication-related AEs, will be summarized by the system organ class and by the preferred term. The severity of event will be recorded once per subject for each term as the maximum severity experienced by each subject (i.e. where the order of most severe to least severe is given by: severe, moderate and then mild).

Summary of AEs by Causality

The number and percentage of subjects reporting AEs will be summarized by the system organ class and by the preferred term. The causality will be recorded once per subject for each term giving the most likely relationship to study medication (i.e. in the order: very likely/certain, probable, possible, unlikely and then unrelated).

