7. GENERAL ANALYSIS CONVENTIONS

All tables, figures and listings will be produced using SAS (v9.4 or a more recent version).

Unless otherwise stated, categorical data will be presented using counts and percentages, whilst continuous variables will be presented using the mean, 95% confidence interval for the mean, standard deviation (SD), median, minimum, maximum, number of subjects (n) and number of missing subjects or data points. Minima and maxima will be quoted to the number of decimal places as recorded in the CRF; means, SDs and medians will be quoted to one further decimal place. Percentages will be rounded to one decimal place.

Subjects who withdraw from the analysis will have their data analyzed to the point of withdrawal. Subjects who complete all required assessments up to and including Day 14 will be eligible for the primary PK population. Other subjects who withdraw from the study will be eligible for the ITT population. Unblinded subjects will continue in study after being unblinded unless noted otherwise.

For the purpose of the statistical analyses visit labels may be used interchangeably as Visit and Day as in the table below regardless of actual timing of study visit. Sensitivity analyses will be performed to address any potential visit timing issues.

Visit Label	Visit 1	Visit 2	Visit 3	Visit 4	Visit 5	Visit 6	Visit 7	Visit 8	Visit 9
Intended Day	Day -28	Baseline, Day 0	Day 3	Day 5	Day 7	Day 14	Day 28	Day 49	Day 140

a. DEFINITION OF STATISTICAL SIGNIFICANCE

- Primary Efficacy Endpoint

The BPL HRIG treatment effect will be considered non-inferior to the active comparator HRIG treatment when the resultant p-value from the one-sided Farrington-Manning

Score Test for proportion difference is [REDACTED].

- Secondary Efficacy Endpoints

The secondary efficacy endpoint analyses will be considered statistically significant using a two-sided significance level of 0.05.

b. ANALYTIC POPULATIONS

The following analysis populations will be defined for this study.

- Intent-to-Treat [ITT] Population

The intent-to-treat (ITT) population will include all randomized subjects. All analyses will be performed using the ITT population.

- Safety Population

The safety population will be defined as all subjects who receive at least one dose of BPL HRIG / comparator HRIG. Safety data will be analyzed up to the point of withdrawal for applicable subjects. The safety population will be used for all safety analyses.

- Per Protocol [PP] Population

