The per protocol population will be split into the **primary** and **secondary** PK populations.

The **primary PK population** will be defined as all subjects who receive the full dose of BPL HRIG / comparator HRIG and the first 3 doses of active rabies vaccine on Visits 2, 3, and 5, and for whom the PK sample at Visit 6 is taken. This population will be used for the primary PK analysis and selected secondary PK analyses. The **secondary PK population** will be defined as all subjects who receive the full dose of BPL HRIG / comparator HRIG and all 5 doses of active rabies vaccine and for whom all required PK samples are taken. This population will be used for selected secondary PK analysis and the exploratory analysis.

Subjects with a pre-dose RVNA of \geq the LLOQ will be excluded from the all

analyses.

[REDACTED]

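### The exclusion of subjects with a quantifiable pre-dose titre from all analyses, read literally, contradicts the ITT and Safety populations; its scope should be stated

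*Protocol*

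**What the plan says.** Three unqualified statements stand together in Protocol 10.4.

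- **ITT:** all randomized subjects, followed by "All analyses will be performed using the ITT population".
- **Safety:** subjects with at least one dose of either HRIG, followed by "The safety population will be used for all safety analyses".
- **Exclusion:** subjects with a pre-dose RVNA at or above "the LLOQ will be excluded from all analyses".

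SAP 7.b repeats all three. For ITT it has "The intent-to-treat (ITT) population will include all randomized subjects". For Safety it has "The safety population will be defined as all subjects who receive at least one dose of" either HRIG product. For the exclusion it has "the LLOQ will be excluded from the all", then the word analyses, and a redacted block follows directly.

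The safety sections rely on the Safety population. Protocol 10.6 states "The safety analysis will be based on the safety population", and in 10.6.1 the denominator for AE percentages "will be the number of subjects in the safety population per treatment group".

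Protocol 8.1.4 puts the LLOQ at about 0.1 IU/mL. It has all of a subject's RVNA samples, including the pre-dose one, tested together after that subject has completed the study. No baseline-titre criterion appears in Protocol 5.2 or 5.3.

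**The concern.** A dosed subject with a quantifiable pre-dose titre belongs to ITT and Safety by definition, yet the exclusion bars that subject from every analysis run on those populations. Both instructions cannot be followed. The result arrives too late to act as an eligibility screen, so the rule can only remove people who have been randomized, given a plasma product and followed.

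What is at stake is mainly safety reporting under Objective 4. On the literal reading, AEs, injection-site findings and laboratory results from dosed subjects drop out of the summary tables, and the subjects drop out of the denominators. Two programmers working faithfully from the same text could produce different safety tables.

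**Working it through.** **1. The passages side by side**

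| Rule | Where | Baseline-titre condition? | Subject dosed, pre-dose RVNA at or above LLOQ |
|---|---|---|---|
| ITT = all randomized | Protocol 10.4, SAP 7.b | None | In |
| Safety = at least one HRIG dose | Protocol 10.4, SAP 7.b | None | In |
| AE denominator = Safety population | Protocol 10.6.1, SAP 8.h | None | In |
| LLOQ exclusion from all analyses | Protocol 10.4, SAP 7.b | Yes | Out |

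The sentence that follows the exclusion in Protocol 10.4 deals with ineligible subjects and major deviations, and it confines itself to the per protocol population by name. The LLOQ sentence does not.

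**2. The plan's own figure**

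The plan attaches no number to this rule. Its sample size of 73 per group (Protocol 10.9) does reproduce, so it is not in question. The inputs are 98% success in both arms, a margin of 0.10, one-sided alpha 0.025 and 85% power. The Farrington-Manning constrained rates are 0.8895 and 0.9895.

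- Null SD: s0 = sqrt(0.8895×0.1105 + 0.9895×0.0105) = 0.3296
- Alternative SD: s1 = sqrt(2×0.98×0.02) = 0.1980
- n = [(1.960×0.3296 + 1.036×0.1980)/0.10]² = 72.4, rounded up to 73

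**3. How many subjects might be affected**

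The documents give no prevalence, so p below is an assumption. With 162 randomized, the expected number is 162p and the chance of at least one is 1 − (1 − p)^162.

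| Assumed p | Expected number | Chance of at least one |
|---|---|---|
| 0.1% | 0.16 | 15% |
| 0.5% | 0.81 | 56% |
| 1% | 1.62 | 80% |
| 5% (upper illustration) | 8.10 | over 99.9% |

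Entry requires no previous rabies exposure, vaccine or immunoglobulin (inclusion c), so the low end is more plausible.

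**4. Effect on safety precision**

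The exact one-sided 95% upper bound for an event not seen among n subjects is 1 − 0.05^(1/n).

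- n = 81: 3.63%
- n = 80: 3.68%
- n = 77: 3.82%

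**5. Effect on the primary comparison**

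The responder counts are assumed: 79/81 (97.5%) per arm, close to the planned 98%. The affected subjects are assumed to be BPL responders only. The limits are asymptotic Farrington-Manning score limits at one-sided 0.025, and p is one-sided against −10%.

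For 79/81 against 79/81, the constrained rates at −10% are 0.8868 and 0.9868. The standard error is sqrt[(0.8868×0.1132 + 0.9868×0.0132)/81] = 0.0374, so z = 0.10/0.0374 = 2.67 and p = 0.0038.

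| BPL after exclusion | Comparator | Lower limit | p |
|---|---|---|---|
| 79/81 (none removed) | 79/81 | −6.4% | 0.0038 |
| 78/80 | 79/81 | −6.5% | 0.0041 |
| 77/79 | 79/81 | −6.6% | 0.0044 |
| 76/78 | 79/81 | −6.7% | 0.0047 |

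Even with all removals in one arm, the limit moves by about 0.3 percentage points and stays well inside −10%.

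**The case against.** The strongest reply is that the sentence was only ever meant for the PK populations. It sits under the Per Protocol heading, after the two PK definitions and before another per-protocol exclusion. The section also uses the phrase all analyses loosely: "All analyses will be performed using the ITT population" cannot be literal either, because Protocol 10.5.1 bases the primary analysis on the primary PK population. Protocol 10.6 and 10.6.1 name Safety as the basis for safety work, and the synopsis population definitions carry no LLOQ exclusion. The SAP redaction may hide a qualification.

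Much of this stands. A PK-only intent is plausible, and the redacted SAP text cannot be assessed. But intent is not wording. The neighbouring sentence names the per protocol population and this one says all. Sections 10.6 and 10.6.1 restate one side of the conflict without settling it. The Protocol text is visible and has no limiting words.

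The reply is also right that the practical harm is small. All data are to be listed (Protocol 10.3), every AE appears in the listings (10.6.1), and SAE reporting under Appendix A does not depend on analysis populations.

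A reader might go further and infer that the rule endangers the non-inferiority conclusion, because an affected subject could also be a non-complier under Protocol 10.7.2 and be set to failure. With the same assumed counts, three BPL responders set to failure would give 76/81 against 79/81 and a limit of −11.5%. The documents do not support charging that to the LLOQ sentence. The figure comes from the worst-case non-complier rule, whereas the LLOQ sentence removes subjects, which gives the −6.5% to −6.7% above. Nor is a quantifiable titre in itself a breach of inclusion (c), so the overlap arises only if prior exposure is established.

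**Conclusion.** The concern holds as a scope error in a stated rule. Read literally, Protocol 10.4 and SAP 7.b remove dosed subjects from the safety summaries and denominators that the same sections say include them. It is minor. The number affected is not given and is probably small, the loss of safety precision is negligible, and the primary result barely changes. Those sizes rest on the assumed prevalence, the assumed 79/81 responders per arm and the one-arm split.

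A reader might also suspect bias. The documents point the other way: the criterion is a pre-dose value, laboratory staff are blinded (Protocol 8.1.4), and treatment stays blinded until after database lock (SAP 4).

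Confidence is moderate, because the placement suggests a PK-only intent and the SAP text after the sentence is redacted.

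**What to change.** Replace the sentence in Protocol 10.4 and SAP 7.b with:

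*Subjects with a pre-dose RVNA at or above the LLOQ will be excluded from the primary and secondary PK populations; they remain in the ITT and Safety populations.*

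If the redacted SAP text already says this, only the Protocol needs the change. The primary analysis is unaffected, because it runs on the primary PK population, where the exclusion stays. The sensitivity analyses need no new text on this account. The cost is one sentence in each document, with no extra data and no change to sample size. It should be settled before unblinding.
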